16.6	Appendix 6: Patient Disease and Treatment Assessment Form (PDF).....	59
16.7	Appendix 7: Fear of Cancer Progression Form.	61

SYNOPSIS AND SCHEMA

Background

Lutetium-177-conjugated prostate-specific membrane antigen (Lu-PSMA) has promising activity and tolerability in single arm studies of men with metastatic castrate resistant prostate cancer (mCRPC) and is currently being examined for efficacy in randomised controlled trials. Enzalutamide is a potent androgen receptor blocker that is already widely used in castration-sensitive and castration-resistant prostate cancer. However, acquired resistance is almost universal and primary resistance occurs in 25% of men with prostate cancer starting enzalutamide.

Pre-clinical data suggest there is a relationship between androgen receptor blockade and PSMA receptor expression. Androgen receptor blockade appears to upregulate PSMA receptor expression, and PSMA receptor blockade, in turn, appears to increase the involutional response of tumour cells to enzalutamide. This is supported by mouse models, which have demonstrated a significant increase in cellular DNA damage in prostate xenografts with the combination treatment of enzalutamide and Lu-PSMA compared to Lu-PSMA alone.

Hypotheses

The combination of Lu-PSMA and enzalutamide may allow synergistic benefit, with enzalutamide treating androgen-signalling inhibitor sensitive clones, and Lu-PSMA treating residual castration-resistant clones. We hypothesise that the combination of Lu-PSMA and enzalutamide may thereby improve outcomes in men with mCRPC with high-risk of progression on single agent enzalutamide.

Aim

To determine the activity and safety of adding Lu-PSMA to enzalutamide in mCRPC not previously treated with chemotherapy; and to identify potential prognostic and predictive biomarkers from imaging, blood, and tissue.

Objectives

Primary

Secondary

To determine the effects of treatment on:

1. PSA Progression Free Survival (PFS, PCWG3)
2. Radiological PFS (RECIST 1.1 and PCWG3)
3. PSA response rate (PSA reduction of $\geq 50\%$ from baseline)
4. Pain response and PFS (PPI scale)
5. Clinical PFS (imaging, symptoms, initiation of new anticancer treatment)
6. Aspects of health-related quality of life (EORTC QLQ-C30, Patient DATA Form, Fear of Cancer Progression short form)
7. Frequency and severity of adverse events (CTCAE v 5.0)
8. Overall survival (death from any cause)
9. Resource use and incremental cost-effectiveness
10. To identify biomarkers from imaging, blood, and tissue associated with prognosis, response to treatment, and/or safety, including:

Tertiary

- i) ^{68}Ga -PSMA PET/CT intensity up-regulation at baseline, Day 15, Day 92 and at first progression (PSA or radiological)
- ii) Associations between quantitative ^{68}Ga -PSMA PET/CT parameters (including ^{68}Ga -PSMA PET avidity) and outcomes
- iii) Associations between ^{68}Ga -PSMA PET avidity to other predictive biomarkers in mCRPC (baseline characteristics, FDG PET/CT, CTC, AR-V7)
- iv) Associations between clinical outcomes and other prognostic and/or predictive biomarkers (tissue and circulating), including circulating tumour cells (CTCs) and circulating tumour DNA (ctDNA)

Design

Population

Phase 2, randomised, 2-arm, multicentre, open-label trial

Men with metastatic prostate cancer, progressing on androgen deprivation therapy, not previously treated with chemotherapy for castration-resistant disease, at high risk of early failure on enzalutamide**, and with PSMA avid disease (SUV max >15 at a single site, and SUV max >10 at all sites >10 mm).

**2 or more of: LDH \geq ULN, ALP \geq ULN, albumin <35 g/L, M1 disease at initial diagnosis, <3 years from initial diagnosis to randomisation, >5 bone metastases, visceral metastases, PSA doubling time <84 days, pain requiring opiates >14 days, prior treatment with abiraterone.

Study treatments

Enzalutamide 160 mg daily orally, continued until disease progression or prohibitive toxicity, PLUS Lu-PSMA (7.5 GBq) on days 15 and 57, with 2 additional doses following central review based on a repeat ^{68}Ga -PSMA PET/CT on day 92 (experimental group).

OR

Enzalutamide 160 mg daily orally, continued until disease progression or prohibitive toxicity (control group).

Assessments

Clinical assessments, HRQL, and PSA at baseline, every 4 weeks on study treatment, then every 6 weeks until radiological progression. Imaging with CT and bone scan at baseline, day 99, then every 12 weeks. Imaging with ^{68}Ga -PSMA at baseline, days 15 and 92 and first progression (PSA or radiological). FDG PET/CT baseline and first progression. PSMA SPECT 24 hours after each dose of Lu-PSMA. Translational research bloods at baseline, day 92, and first progression. Biopsies for research performed at baseline and first progression in consenting patients (optional).

Statistical considerations

Randomisation (1:1) to enzalutamide plus Lu-PSMA versus enzalutamide alone. A sample size of 160 participants recruited over 12 months and followed until 150 events have occurred (approximately 18 months extra), would provide 80% power at the two-sided 5% level of significance to detect a HR of 0.625 assuming a median PSA PFS of 5 months in the enzalutamide alone arm, whilst allowing for non-adherence to assigned treatment in up to 2 participants.

[figure not shown]
Study Schema*

Eligibility

Confirmed mCRPC with PSA rising and ≥ 5 ng/mL
No chemotherapy for mCRPC
 ≥ 2 high risk features for early failure on enzalutamide
Baseline PSMA SUV max > 15 on ^{68}Ga -PSMA PET/CT

Stratification

Study site
Volume of disease (> 20 vs ≤ 20 sites)
Early docetaxel for castration-sensitive disease (Y/N)
Prior treatment with abiraterone (Y/N)

* Refer to section 6.2.3 for translational research components schema

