6 ASSESSMENT PLAN

6.1 Schedule of Assessments

Stage	Screening	Baseline	On study treatment	At First Progression (PSA or radiological) ¹ AND End of Treatment for reasons other than progression	After last dose of study treatment		
Timing	Within 28 days prior to randomisation	Within 7 days prior to randomisation	All participants Day 15, then 4 weekly (\pm 7 days) ⁸	\pm 7 days	42 days and 84 days after last dose of study treatment (\pm 7 days)	Until radiological progression (6 weekly \pm 7 days)	After radiological progression (12 weekly \pm 7 days)
Informed consent (including Medicare consent)	X						
Medical oncology assessment ²	X	X ⁹	X	X	X	X	
Blood tests ³	X	X ⁹	X	X	X	X	
PSA	X	X ⁹	X	X	X	X	
Translational research bloods ^{4a}		X ^{4b}	Day 92 only	At first progression only, before subsequent therapy ⁵			
⁶⁸ Ga-PSMA PET/CT	X		Days 15 and 92	X (At progression only) ⁵			
¹⁸ F FDG PET/CT	X			X (At progression only) ⁵			
SPECT CT			24hrs post Lu-PSMA				
CT CAP / Whole body bone scan ⁶	X		Day 99, then 12 weekly thereafter	X		12 weekly until radiological progression	
Tissue biopsy ^{4a}		Optional ^{4c}		Optional (At progression only) ⁵			
Adverse events ⁷			X	X	X		
Compliance			Days 15 and 43				
Concomitant medications				Within 30 days prior to an SAE			
HRQL forms		X ¹⁰	X (not day 15)	X	X	X	
Fear of Cancer Progression Short Form		X ¹⁰					
Survival and Subsequent Treatment					X	X	X

Notes

1. Refer to section 7.1 for definition of PSA progression or 7.2 for definition of Radiological progression.
2. Clinical assessment includes history (at baseline) and physical examination, performance status and weight. All visits after baseline include a review of any adverse events and physical examination as per standard of care for a participant at this stage of their disease and treatment
3. Blood tests include the following:
 - Haematology: Complete blood examination (CBE): haemoglobin concentration, white cell count, platelet count, white cell differential.
 - Biochemistry: Electrolytes, urea, creatinine (EUC); liver function tests (LFT): bilirubin, alkaline phosphatase (ALP), alanine aminotransferase (ALT), gamma glutamyl transferase (GGT), lactate dehydrogenase (LDH; screening only)
4. a. Refer to Biological Sampling Manual for details of collection, processing and shipping procedures.
b. Baseline TR blood draw after randomisation, within 7 days prior to commencing study treatment.

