c. Baseline tissue biopsy (optional) may occur any time after patient consents (pre- or post-randomisation), but prior to commencing study treatment. Refer to the Biospecimen Sampling Manual for details.
5. PSA progression and radiological progression may occur at different times. If so, then ⁶⁸Ga-PSMA PET/CT, ¹⁸F FDG PET/CT, translational research blood collection and tissue biopsies (optional) are only required to be completed at first documented progression (either PSA or radiological, whichever occurs first).
6. Imaging must include a CT of the chest, abdomen and pelvis, and a radio-isotope whole body bone scan (WBBS). If screening FDG PET imaging includes a diagnostic CT, then a separate baseline CT is not required. 12-weekly imaging with CT and WBBS should continue until radiological progression is documented per RECIST 1.1 or PCWG3 (see section 7.2), even if new anticancer treatment is commenced earlier.
7. Adverse events categorised and graded according to CTCAE v5.0 and should continue to be recorded until 12 weeks after the study treatment ends.
8. For Day 15 assessments a window of +7 days only is permitted, with the exception of the Day 15 ⁶⁸Ga-PSMA PET which has a -5/+7 day window
9. If screening medical oncologist assessment, blood tests and PSA were completed within 7 days prior to randomisation, then they do not need to be repeated.
10. Baseline HRQL forms and Fear of Cancer Progression Short Form can be completed within 7 days pre- or post-randomisation, prior to commencing study treatment.

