6.4 Follow-Up after Study Treatment Discontinuation

Study-specific follow-up assessments should be completed at the specified time points (± 7 days). Participants who stop study treatment prior to the time recommended in the protocol will continue follow-up visits according to the protocol.

If a participant wishes to stop the study visits, they will be requested to allow their ongoing health status to be periodically reviewed via phone contact or from their general practitioner, or medical records.

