7 OUTCOMES, ENDPOINTS AND OTHER MEASUREMENTS

7.1 PSA Progression-Free Survival (PCWG3)

The primary endpoint of this study is PSA progression-free survival defined as the interval from the date of randomisation to the date of first evidence of PSA progression or the date of last known follow-up without PSA progression.

PSA progression is defined as a rise in PSA by more than or equal to 25% AND more than or equal to 2 ng/mL above the nadir (lowest PSA point). This needs to be confirmed by a repeat PSA performed at least 3 weeks later.

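### PSA collection ends within about 12 weeks of radiological progression, although confirmed PSA progression is the only primary event, so the 150-event target may be out of reach

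*Protocol*

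**What the plan says.** **Endpoint.** Protocol section 7.1 runs the primary endpoint from randomisation to the "date of first evidence of PSA progression or the date of last known follow-up without PSA progression". A qualifying rise counts only once repeated: "This needs to be confirmed by a repeat PSA performed at least 3 weeks later". Radiographic progression is a separate secondary endpoint (7.2).

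**PSA schedule.** The synopsis gives "Clinical assessments, HRQL, and PSA at baseline, every 4 weeks on study treatment, then every 6 weeks until radiological progression", and section 6.2.1 ends clinic review at the same point. The table in section 6.1 is more generous. It marks PSA at the first-progression or end-of-treatment visit, and again at "42 days and 84 days after last dose of study treatment", without regard to progression status. In the final column, headed "After radiological progression (12 weekly" visits, the PSA row is blank and only survival and subsequent treatment are marked.

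**Imaging schedule.** Note 6 to the same table says "12-weekly imaging with CT and WBBS should continue until radiological progression is documented", and it applies even when new anticancer treatment starts earlier.

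**Treatment.** Imaging progression is a form of clinical progression (7.5), and clinical progression ends study treatment (5.7). PSA progression alone does not.

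**Sample size.** Section 13.1 plans 160 men, 12 months of recruitment and follow-up to 150 events (about 18 months more), for 80% power at two-sided 5% to detect a hazard ratio (HR) of 0.625 with a control median of 5 months. The only allowance is for non-adherence in up to 2 participants.

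**The concern.** Follow-up for the primary endpoint is tied to a different endpoint. The protocol expects the two progressions to occur at different times (note 5 to the table in 6.1). A man whose scan progresses first has not had a primary event. His treatment stops, he has PSA scheduled at about 6 and 12 weeks after his last dose, and then none. If his PSA progresses later, the trial does not see it. A rise first seen at day 84 has no scheduled confirmatory sample, although 7.1 requires one. A man who stopped treatment more than 84 days before his scan progressed has no scheduled PSA after the progression visit.

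Two things are at stake. First, the design needs nearly every man to have an observed event, and an analysis plan cannot recover PSA values that were never taken. Second, the censoring date in 7.1, "the date of last known follow-up without PSA progression", could be read as the last contact of any kind. Survival contacts continue every 12 weeks without PSA, and men who decline study visits may be "periodically reviewed via phone contact or from their general practitioner, or medical records" (6.4). On that reading, men are counted as free of PSA progression over time in which PSA was not measured.

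**Working it through.** **1. The planned event number reproduces.** With (1.960 + 0.842)² = 7.849:
- Freedman: 7.849 × (1.625/0.375)² = 147.4, so 148 events.
- Schoenfeld: 4 × 7.849/(ln 0.625)² = 31.40/0.2209 = 142.1, so 143 events.
- With 2 of 160 men non-adherent, the HR dilutes to 0.625 + 0.375 × 2/160 = 0.630. The two formulas then give 153 and 147, which bracket the planned 150.

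**2. Events expected with full PSA follow-up.** Assume exponential times with medians of 5 and 5/0.625 = 8 months, so λ = 0.1386 and 0.0866 per month. Recruitment is uniform over A = 12 months, followed by F = 18 more. The proportion with an event in each arm is 1 − (e^(−λF) − e^(−λ(F+A)))/(λA):
- Control: 0.960 × 80 = 76.8.
- Combination: 0.869 × 80 = 69.5.
- Total: 146 events at month 30, and about 150 at month 33 (F = 21).

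Power is Φ(√d × 0.470/2 − 1.96). At d = 146 it is 0.81. The fair comparator at month 30 is therefore 146, not 150.

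**3. The ceiling.** 150/160 = 93.75%, which leaves room for 10 men without an event. Let q be the share whose PSA follow-up ends before PSA progression (not given in the documents; assumed 3% to 25%). The ceiling is 160(1 − q). The month-30 columns treat the loss as independent of PSA progression.

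| q | Ceiling | Events at month 30 | Power at month 30 |
|---|---|---|---|
| 3% | 155 | 143 | 0.80 |
| 6.25% | 150 | 139 | 0.79 |
| 10% | 144 | 134 | 0.78 |
| 20% | 128 | 122 | 0.74 |
| 25% | 120 | 115 | 0.71 |

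Above 6.25%, 150 events cannot be reached however long the trial runs.

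**4. Simulation of the section 6.1 schedule.** PSA and radiographic times are exponential and linked by a Gaussian copula. Scans are at Day 99 and every 84 days after that. PSA is available until 84 days after the scan that shows progression. The PSA values are those of the plan. Assumed, because the documents give none of them: control radiographic median 6 to 12 months, radiographic HR 0.625 to 1.0, correlation 0 to 0.8. Results with censoring at the last PSA:

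| Correlation | Events at month 30 | Power | HR (true 0.625) |
|---|---|---|---|
| 0 | 108–126 | 0.69–0.75 | 0.62–0.63 |
| 0.5 | 115–135 | 0.71–0.78 | 0.61–0.63 |
| 0.8 | 123–143 | 0.74–0.80 | 0.58–0.63 |

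Power is the Schoenfeld value at HR 0.625 for each event count. A simpler model, with continuous detection and radiographic medians 1.5 to 3 times the PSA medians, gives 111 to 143 events.

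The control median stays at 5.0 months. The first scan is at Day 99, so PSA runs to at least day 99 + 84 = 183, about 6.0 months, which is beyond the median. The combination median moves by half a month at most.

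**5. The same model with censoring at last contact.** The HR ranges from about 0.56 to 0.72 (end points good to about 0.01), and the combination median is up to about 1 month too long (true value 8.0). The HR moves towards 1 when the correlation is zero. It falls furthest below 0.625 when the correlation is high and the treatment has no radiographic effect. The direction is therefore not known in advance.

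**The case against.** **PSA does not stop at radiological progression.** This is correct, and a reader of the synopsis alone would be misled. Section 6.1 keeps PSA at the progression or end-of-treatment visit and at 42 and 84 days after the last dose. Those two samples are far enough apart to satisfy the 3-week confirmation rule. The 4-weekly on-treatment column has no cut-off at radiological progression. The window may be longer still, because the criteria in Appendix 3 ask for confirmatory scans at least 6 weeks later. The simulation already credits 84 days but not that extra period.

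**A reader might infer that the events are lost informatively and that the treatment effect is therefore biased.** The documents do not support that as a firm claim. The heaviest losses occur at zero correlation, where censoring at the last PSA leaves the HR unbiased. Where correlation is high, fewer events are lost. If the radiographic effect equals the PSA effect (HR 0.625), the estimated HR stays at about 0.62 to 0.63 at every correlation.

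**Censoring dates belong in the analysis plan.** In part. The wording in 7.1 can equally mean the last PSA without progression, and a later plan could settle it. No plan can replace missing PSA values, and the visit schedule is fixed in the protocol.

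**PSA taken after new treatment reflects that treatment.** This is true, and it is a real choice about what the endpoint measures. Note 6 already makes that choice for scans, and 13.2 adopts the intention-to-treat principle. A sensitivity analysis can show how much it matters.

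**Conclusion.** The point stands in a limited form. Primary-endpoint follow-up ends, apart from the visits up to 84 days after the last dose, at an event that is not a primary event, and the sample size has no allowance for this. The arithmetic limit is firm: more than 10 men lost in this way puts 150 events out of reach. The size of the loss is not firm, since it rests on an assumed radiographic median, radiographic effect and correlation. Over the ranges shown, events at month 30 fall from 146 to about 108 to 143, and power from 0.81 to about 0.69 to 0.80. At the favourable end the cost is negligible.

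Bias in the HR and the medians is a secondary matter. It is small if men are censored at the last PSA and larger if they are censored at last contact. Its direction cannot be stated from the documents.

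**What to change.** 1. In section 6.1, continue PSA until confirmed PSA progression or death, regardless of radiological progression or new anticancer treatment, as note 6 does for scans. Routine local results suffice.
2. In section 7.1, state that men without confirmed PSA progression are censored at the last evaluable PSA.
3. Reconcile the synopsis and section 6.2.1 with section 6.1, so that all three give the same PSA schedule.
4. Add a sensitivity analysis that censors at the start of new anticancer treatment.

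The cost is a row in the schedule, one definition and a few more routine PSA results per man, with no new procedure. The drawback is that some of these values will be taken under later treatment, which item 4 addresses.

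If PSA is not extended, restate the event target and power in section 13.1 with an explicit allowance for men whose PSA follow-up ends before the event. Item 2 is needed either way.

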1 BACKGROUND

1.1 Prostate Cancer

Metastatic prostate cancer is the second most common cause of cancer death in Australian men, and despite the plethora of new treatments that have been developed and evaluated in the last decade, this disease almost invariably progresses and remains lethal. While there are a number of new treatments available for men with metastatic prostate cancer, optimal sequencing of these treatments remains unclear. Further, men and their doctors lack prospectively validated predictive biomarkers that can optimise personalised therapy or guide combination therapy choices. This is the concept of precision medicine.

In the last few years significant work has been undertaken evaluating imaging and therapy techniques that utilise a prostate cancer specific peptide (e.g. PSMA) which precisely target prostate cancer cells (1-13). These theranostic agents (such as the PSMA imaging and therapy partners), are unique in their ability to not only visually identify prostate cancer phenotypes that will respond to targeted therapy but also demonstrate patterns of disease response allowing decisions regarding subsequent treatment options(6).

Two prospective single site targeted radionuclide therapy trials using ¹⁷⁷Lu PSMA -617 (9, 10) and multiple retrospective trials (14-21) in the last few years in men who have failed chemotherapy are looking very promising and raise the question as to whether targeted radionuclide therapy may be more beneficial if given to men earlier in the metastatic disease journey – especially to those in the pre-chemotherapy space. Given the potential synergies in mechanisms already demonstrated in preclinical work (13), combination therapies that improve treatment response without increasing toxicity may extend these benefits even further, particularly in those men at high risk of early treatment failure.

1.2 Androgen Receptor Signalling Inhibition

Enzalutamide is a targeted androgen-receptor inhibitor that competitively binds to the ligand-binding domain of the androgen receptor and inhibits androgen-receptor translocation to the cell nucleus, recruitment of androgen-receptor cofactors, and androgen-receptor binding to DNA. Enzalutamide improved survival in men with mCRPC that had progressed after chemotherapy (22). Subsequently, in a double-blind, phase 3 study (PREVAIL) comparing enzalutamide with placebo in the pre-chemotherapy setting, enzalutamide significantly decreased risk of radiographic progression and death while delaying initiation of chemotherapy in men with mCRPC (23). However, there is a significant proportion of men who fail to derive prolonged benefit from androgen signalling inhibition with enzalutamide, with 50% of men demonstrating PSA progression by 11 months (23).

Risk factors that help to predict poor responses to enzalutamide include the presence of AR-V7 splice variants, anaemia, radiographic progression prior to commencing treatment, elevated LDH or ALP, rapid PSA velocity, liver metastases and short time since diagnosis. In men with these risk factors, median time to PSA progression can be as short as 5.6 months (IQR 3.4-8.3) compared to 14.5 months (IQR 11.3-19.1) for men without these risk factors (24). The PROPHECY trial presented at the 2018 ASCO ASM evaluated the ability of AR-V7 splice variants to predict treatment response to enzalutamide in men with mCRPC who had 2 or more high risk features. The presence of AR-V7, as detected using the EPIC CTC AR-V7 assay, independently predicted both a shorter overall survival (OS) and a shorter radiographic progression free survival (rPFS) in men receiving enzalutamide. Though this biomarker appears to predict for a shorter duration of benefit, lack of a

proven alternative strategy renders this knowledge prognostic at best and therefore does not improve treatment outcomes. However, if AR-V7 was found to have a strong correlation to PSMA expression and upregulation, combination therapy using androgen signalling inhibition and PSMA targeted therapy could well improve treatment response in those men who are AR-V7positive and predicted to have a poor response to enzalutamide alone.

